2.7 Statistical Analysis and Sample Size Justification	
The data will be analyzed by the Investigator and Co-investigator.
 
Main outcomes will be ISI, CAPS nightmare frequency and total score, diary and PSG sleep latency and WASO at week 3 and for non-PSG variables Med week 6. We will also explore effects on REM and SWS and their relationships to other study outcomes.
 
An alpha level of .05 (one-tailed) will be applied in testing Hypotheses 2a), 2b), 2d), and 2e). Initially, data will be pre-screened for errors, outliers, normality of distributions, and any necessary modifications, such as transformation of variables and/or elimination of cases, will be conducted.
 
Our initial objectives are descriptive. We will generate frequencies of types of trauma exposures associated with insomnia and the rates for PTSD diagnoses and sub-diagnostic threshold PTSD symptoms in the recruited study population (Objective 1) and the frequency of adverse events (Objective 2). The latter will be descriptively contrasted to the extant data for suvorexant from the insomnia registry trials as a guide to planning future trials including dosing.
 
Hypothesis 2a) Insomnia will improve, and nightmares and other PTSD symptoms will be reduced with suvorexant treatment compared with placebo: We will compare baseline characteristics of the treatment groups using independent samples t-tests for continuous variables or chi-square tests for categorical variables. If a significant group difference is found in some of the variables, the variable(s) will be included in subsequent analyses as a covariate(s). We will perform 2 (Group) x 3 (Time: baseline, Med week 3, and week 6) mixed ANOVAs or ANCOVAs [if there is a covariate(s)] to compare the changes in ISI scores, nightmare frequency, and CAPS scores, separately, between the two groups.
 
Hypothesis 2b) Improved sleep will be associated with reduced non-sleep PTSD symptoms: Correlation coefficients between baseline – Med week 6 changes in sleep measures (e.g., ISI scores and nightmare frequency) and changes in the CAPS scores excluding two sleep-related items will be computed. In addition, we will exploratively examine if there is an interaction with treatment condition by performing regression analyses in which CAPS scores will be predicted by changes in sleep measures, treatment condition, and a Sleep measure X Treatment condition interaction.
 
Hypothesis 2d) Sleep latency and wake after sleep onset (WASO) will be reduced with suvorexant treatment compared with placebo: We will perform 2 (Group: suvorexant vs. placebo) x 2 (Time: Baseline and Med week 3) mixed ANOVAs or ANCOVAs [if there is a covariate(s)] to compare the changes in PSG measured sleep latency and WASO between the suvorexant and placebo groups.
 
Exploratory hypothesis 2e) When reduced at baseline (i.e., SWS below 100 minutes and mean REM segment duration below 15

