
	
minutes), SWS and the duration of continuous segments of REM sleep will increase with suvorexant than placebo: Participants with reduced baseline SWS (below vs. above 100 minutes) and mean REM segment duration (below vs. above 15 minutes) will be included in the analyses. 2 (Group) x 2 (Time: Baseline and Med week 3) mixed ANOVAs or ANCOVAs will be performed to compare treatment changes in SWS and REM segment duration between the suvorexant and placebo groups.
 
Power Considerations:
 
G*Power 3.1 ³³ was used to conduct power analysis.
 
Power analysis for Hypothesis 2a) is based on the effect size estimated using findings of Herring and colleagues' ²² placebo controlled trial of suvorexant in adults with insomnia. Since there are no data for suvorexant on trauma related nightmares and PTSD symptoms, we also used Taylor and colleagues' ²⁴ placebo controlled trial of prazosin in civilian outpatients with PTSD, sleep disturbances, and nightmares. Taylor et al. found a large-size effect of prazosin on changes in trauma-related nightmare severity compared with placebo ($d = 0.96$ or $f = 0.48$) and PTSD severity ($d = 0.79$ or $f = 0.40$) and a medium-size effect on changes in trauma-related insomnia symptoms severity ($d = 0.50$ or $f = .25$). Herring and colleagues found a small-size effect of a 1-month suvorexant treatment (20mg for nonelderly and 15mg for elderly) on insomnia severity measured by the ISI ($d = 0.39$ or $f = 0.20$). To detect an $f = 0.20$ Group x Time interaction effect in the proposed mixed ANOVA with 80% power, a total of 42 participants are needed.
 
Power analysis for Hypothesis 2b) is based on the effect sizes estimated using Krakow and colleagues' findings ³⁴ from their study examining effects of cognitive behavioral therapy for nightmares and insomnia in crime victims with PTSD. They found correlations between changes in nightmare frequency, insomnia severity, and sleep quality and changes in overall PTSD symptom severity ranging from $r = .37$ to $.40$. A sample size of 43 will allow for detecting similar size effects with 80% power.
 
Power analysis for Hypothesis 2d) is based on findings from the aforementioned Herring and colleagues' study. They found that effects of suvorexant on sleep latency and WASO were $f = 0.17$ and 0.31, respectively. To detect an effect size of 0.17 using the proposed mixed ANOVA with 80% power, a total of 70 participants are needed.
 
Power analysis for Exploratory hypothesis 2e) is based on findings from the aforementioned Taylor and colleagues' study. They found that the effect of prazosin on mean REM period duration was $f = 0.50$. Using the proposed mixed ANOVA, a total of 16 participants will allow for detecting a large size within-between interaction effect ($f = 0.50$) with 80% power.

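### The ISI power calculation enters a two-group f = d/2 as the Group x Time interaction f: for d = 0.39 in change-score SD units the planned 2 x 3 test has about 23% power at 42 participants, not the stated 80%, and about 37% at the 70 to be retained.

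*Combined protocol and SAP*

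**What the plan says.** All of this is in section 2.7, apart from the recruitment target in section 2.5.

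- **Planned test for Hypothesis 2a.** "We will perform 2 (Group) x 3 (Time: baseline, Med week 3, and week 6) mixed ANOVAs or ANCOVAs", run separately for ISI, nightmare frequency and CAPS.
- **ISI effect size.** The cited suvorexant trials are said to show a small effect on "insomnia severity measured by the ISI ($d = 0.39$ or $f = 0.20").
- **ISI sample size.** For f = 0.20 the plan states: "Group x Time interaction effect in the proposed mixed ANOVA with 80% power, a total of 42 participants are needed". The software is G*Power 3.1. The correlation among repeated measures and the effect-size option are not given.
- **Other effect sizes.** The cited prazosin trial supplies d = 0.96 or f = 0.48 for nightmares, d = 0.79 or f = 0.40 for PTSD severity, and "a medium-size effect on changes in trauma-related insomnia symptoms severity ($d = 0.50$ or $f = .25").
- **Hypothesis 2d (PSG, 2 x 2 ANOVA).** The "effects of suvorexant on sleep latency and WASO were $f = 0.17$ and 0.31, respectively". No d is printed. Then: "To detect an effect size of 0.17 using the proposed mixed ANOVA with 80% power, a total of 70 participants are needed".
- **Hypothesis 2b (correlations of .37 to .40).** "A sample size of 43 will allow for detecting similar size effects with 80% power".
- **Alpha.** "An alpha level of .05 (one-tailed) will be applied in testing Hypotheses 2a), 2b), 2d), and 2e").
- **Target.** Section 2.5 recruits 90 to retain 70 and refers to the power analysis.

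**The concern.** All four printed d/f pairs follow f = d/2 after rounding: 0.96/2 = 0.48, 0.79/2 = 0.395, 0.50/2 = 0.25, 0.39/2 = 0.195. That rule holds for two groups compared once. The interaction f is a different quantity: it is what remains of the group-by-time cell means after the group and time main effects are removed, averaged over all cells, including a baseline at which randomised groups should not differ. The same treatment effect therefore gives a much smaller f on the interaction scale.

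ISI is listed first among several unranked main outcomes. A reader who accepts 80% power at 42 will take 70 completers to be ample for it. If the true power is well under one half, an ISI effect of the cited size would probably be missed, and a null result would be read as far stronger evidence of no benefit than it is.

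**Working it through.** **Inputs.** From section 2.7: d = 0.39, f = 0.20, 2 groups, 3 times, N = 42; f = 0.17, 2 times, N = 70. Assumed because not stated: 1:1 allocation, equal variances and correlations across visits (sphericity), correlation ρ = 0.5 except where varied.

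**1. Reproducing the plan's figures.** For k = 2 groups and m times, the Group x Time test has λ = f²·N·m/(1 − ρ), df1 = m − 1, df2 = (N − 2)(m − 1). At alpha .05 and ρ = 0.5:

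- f = 0.20, m = 3, N = 42: λ = 0.04 × 42 × 3/0.5 = 10.08, df 2 and 80, power 80.3%. N = 40 gives 78.2%, so 42 is the smallest even N. N = 70 would give 96.1%.
- f = 0.17, m = 2: 78.9% at 68 and 80.1% at 70.

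Both stated sizes follow if the printed f is entered directly as the interaction f.

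**2. The interaction f that matches d = 0.39.** For group differences p over the three visits, f = √mean[((p − p̄)/2)²], in SD units of a single visit. At ρ = 0.5 the SD of a change score equals the SD of a single visit, so the two scales of d coincide.

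- Full effect at weeks 3 and 6, p = (0, d, d): f = d/√18 = 0.39/4.243 = 0.092.
- Effect building linearly, p = (0, d/2, d): f = d/√24 = 0.39/4.899 = 0.080.
- Conversely, f = 0.20 under the first pattern needs d = 0.20 × 4.243 = 0.85.

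**3. Power of the planned ISI test, d in change-score SD units.** For the first pattern λ = N·d²/3 whatever ρ is: 42 × 0.1521/3 = 2.13 and 70 × 0.1521/3 = 3.55.

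| Pattern | Alpha | N = 42 | N = 70 |
|---|---|---|---|
| Full effect at weeks 3 and 6 | .05 | 23.0% | 36.6% |
| Linear to week 6 | .05 | 18.2% | 28.3% |
| Full effect at weeks 3 and 6 | .10 | 34.2% | 49.4% |

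Simulation of 40,000 trials at ρ = 0.5 and alpha .05 gave 22.8% and 37.0% (full) and 18.1% and 27.9% (linear). Rounding of d (0.385 to 0.395) moves the 36.6% only between 35.8% and 37.5%.

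**4. If d is in raw SD units.** Power at 70 (full effect, alpha .05) is 27%, 37%, 57% and 75% at ρ = 0.3, 0.5, 0.7 and 0.8. Reaching 80% needs ρ of about 0.82 at 70 or 0.89 at 42.

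**5. A simpler test.** A single baseline-to-follow-up comparison of change at 70, which is not the planned test, has 49% power one-tailed and 36% two-sided (change-score units).

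**6. Other Hypothesis 2a effects at 70.** Same method, full effect (linear in brackets): insomnia d = 0.50, 56% (44%); PTSD severity 0.79, 93% (84%); nightmares 0.96, 99% (95%).

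**7. Detectable difference in change at 70 with 80% power.** 0.65 SD for the 2 x 3 test (0.75 SD at week 6 if linear); 0.60 SD one-tailed or 0.68 SD two-sided for a 2 x 2 test.

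**8. Sleep latency and WASO, conditional.** Only if 0.17 and 0.31 are also d/2 (d = 0.34 and 0.62, change-score units), power at 70 is 41% one-tailed (29% two-sided) for sleep latency and 82% (72%) for WASO.

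**9. Alpha.** The 43 for Hypothesis 2b fits one-tailed .05 (r = .37: 80.2%; two-sided 70.0%). At ρ = 0.5 the 42 and 70 are non-directional F tests at .05. Alpha .10 with ρ = 0.37 also returns 42 and 70, so the document does not settle which was used. A 2-df interaction has no one-tailed form.

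**The case against.** - **The scale of d = 0.39 is not documented.** Section 2.7 speaks of effects on changes for the prazosin trial, but for ISI only of an effect on severity. This stands, and in raw SD units a high correlation would narrow the gap. It does not rescue the 42: that would need ρ of about 0.89, and at that value an interaction f of 0.20 would call for only 12 participants, so it cannot be how 42 was obtained.
- **The time pattern is assumed.** True; the cited ISI effect is at one month, between the two visits. Both patterns tried leave power far below 80%.
- **80% for ISI is printed only at 42.** Correct. The 37% at 70 is the power at the planned retained sample and contradicts no printed figure; the 96% is what the plan's own input implies there.
- **The reproduced settings do not explain every sample size.** At ρ = 0.5 and alpha .05, exploratory Hypothesis 2e (f = 0.50) needs 12 participants, not the stated 16. This stands as a further sign that the settings are undocumented, but it does not bear on ISI.
- **The 42 does not set enrolment.** Also true. The 70 comes from sleep latency, where the error cannot be shown, and nightmares and PTSD severity remain well powered at 70 if the prazosin effects carry over. That limits the consequence to what is claimed for ISI, and possibly for sleep latency.

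**Conclusion.** The concern holds. The 42 is correct arithmetic for an interaction f of 0.20, but that f does not represent d = 0.39. In change-score SD units, at alpha .05 and under sphericity, the planned ISI test has about 23% power at 42 and 37% at 70 with the full effect at both visits, and 18% and 28% if it builds linearly. At 37%, a true effect of the cited size would be missed about 6 times in 10. Neither a more lenient alpha nor a single-contrast test brings power to 80%; only a high correlation combined with raw SD units would.

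For sleep latency the point is open: if f = 0.17 was derived as an interaction f, the 70 stands; if it is d/2, it does not. The mixed alpha convention is a minor point of clarity and does not cause the shortfall.

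**What to change.** Rewrite the power paragraph in section 2.7:

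1. Withdraw the statement that 42 participants give 80% power for ISI. State the assumed correlation and, after checking the source, whether d is in change-score or raw SD units. If change-score, for example: *For ISI (d = 0.39 in change-score SD units), the planned 2 x 3 Group x Time test at alpha .05 has about 37% power with 70 completers if the full effect is present at weeks 3 and 6, and 28% if it builds linearly. It has 80% power for a difference in change of about 0.65 SD.*
2. State how f = 0.17 and 0.31 were derived. If as interaction f, keep 70. If as d/2, restate power at 70 as about 41% one-tailed (29% two-sided) for sleep latency and 82% (72%) for WASO, with 80% power for a difference in change of about 0.60 SD one-tailed or 0.68 SD two-sided.
3. State one alpha convention for 42, 43 and 70, and how it applies to a 2-df interaction. The 16 for Hypothesis 2e could be covered in the same sentence.

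The cost is wording, and a less favourable stated power for ISI and perhaps sleep latency. No extra participants, visits or procedures are needed, and the analysis does not change.

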--	--

Adverse Event Screening At each medication visit participants will be queried regarding the presence of any new symptoms or concerns. We will specifically query the adverse effects that occurred at a frequency that exceeded placebo in either the 3 month pivotal trials²² or the 1-year study²³ including somnolence, fatigue, dry mouth, dyspepsia, and peripheral edema. We will also specifically query the pre-specified events of interest for those trials including suicidal ideation, complex sleep-related behaviors (e.g. getting food during the night and not remembering it), sleep onset or off-set hallucinations, sleep paralysis, and falls. Excessive daytime sleepiness will be assessed by administering the Epworth Sleepiness Questionnaire.³¹ Weight and vital signs will be obtained at each study visit. At the post-treatment visit specific inquiry will also include the occurrence of common medication withdrawal symptoms such as dizziness, shaking, nausea, and muscle tension as well as re-assessment of insomnia and sleep patterns for that period.

Polysomnography (PSG):

PSG collection includes a standard electroencephalogram (EEG) montage with two central, frontal, and occipital leads, two electrooculograms, chin and limb electromyograms, and an electrocardiogram (ECG). Recordings will be conducted using an Embla (Denver, CO) Titanium unit in the CRU. Screening for sleep disordered breathing and limb movements will be performed using the screening night data. Visual scoring of sleep records from a computer monitor will be done following the American Academy of Sleep Medicine (AASM) Manual, Version 2.0.³² The REMLogic software (Embla) will calculate sleep parameters including TST, SOL, WASO, the percentage of each sleep stage, and mean duration of continuous REM segment. Calculation of REM segment length used our previous criteria¹⁶ of at least two epochs of consecutive REM sleep with no more than one 30-sec epoch of non-REM sleep interruption. The sleep parameters for baseline will be obtained from the second night recording after an accommodation recording that will also screen for apnea will be used in data analysis. Respiratory strain gauge, nasal air flow, and oximetry monitors will be included on the first but not subsequent nights. Participants will be instructed to go to bed near their habitual bedtimes and will wake up naturally. PSG will be done prior to medication and after 3 weeks of medication treatment to allow for stable dosing.

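### The 16 participants stated for exploratory Hypothesis 2e at f = 0.50 and 80% power are not reproduced by the settings that give the plan's 42 and 70 (these give 12, and 16 gives about 96%), and the power statement includes no effect for slow wave sleep

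*Combined protocol and SAP*

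**What the plan says.** Section 2.7 names G*Power 3.1 as the software for all power calculations. For exploratory Hypothesis 2e the planned analysis is: "2 (Group) x 2 (Time: Baseline and Med week 3) mixed ANOVAs or ANCOVAs will be performed to compare treatment changes in SWS and REM" (for REM, the outcome is the length of its segments), in participants whose baseline value is low (SWS under 100 minutes, mean REM segment under 15 minutes).

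The power paragraph for 2e takes one effect from a placebo-controlled prazosin study, where "the effect of prazosin on mean REM period duration was" f = 0.50. It then states: "Using the proposed mixed ANOVA, a total of 16 participants will allow for detecting a large size within-between interaction effect", at f = 0.50 and 80% power.

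Three other statements bear on this:

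- The same section gives two more mixed-ANOVA figures: 42 for 2a (f = 0.20, 2 groups by 3 times) and 70 for 2d (f = 0.17, 2 groups by 2 times), both at 80% power.
- On significance level it says: "An alpha level of .05 (one-tailed) will be applied in testing Hypotheses 2a), 2b), 2d), and 2e").
- Section 2.5 (Polysomnography) defines this trial's REM outcome: "Calculation of REM segment length used our previous criteria", namely at least two consecutive REM epochs with at most one interrupting 30-second epoch.

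No correlation between repeated measures is given for any of these calculations. Section 2.7 gives no SWS effect size and no forecast of how many participants will fall in the low-baseline subset.

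**The concern.** An f of 0.50 is a large effect, and with two time points the within-between interaction test in G*Power needs very few participants to detect it. Sixteen looked too many for 80% power beside the plan's 42 and 70.

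The paragraph also speaks for 2e as a whole, although 2e has two outcomes and only one of them has an effect behind it.

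The stake is limited but real. The size of the 2e subset is unknown until baseline polysomnography has been read, and 16 is the only figure in the plan against which a reader could judge whether that subset is adequate. A reader could also set an inconclusive SWS result against an 80% that was never calculated for SWS.

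**Working it through.** **Method.** The G*Power procedure for a repeated-measures within-between interaction uses a noncentral F with

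- λ = f² × N × m / (1 − ρ)
- df1 = (k − 1)(m − 1)
- df2 = (N − k)(m − 1)

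where k is the number of groups, m the number of time points and ρ the correlation between repeated measures (sphericity assumed). From section 2.7: f, k = 2, m, and 80% power. Not stated: ρ.

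**Step 1: reproduce the plan's other figures.** Take ρ = 0.5 and an F test at .05.

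| Hypothesis | f | m | N | λ | df | Power |
|---|---|---|---|---|---|---|
| 2a | 0.20 | 3 | 42 | 0.04 × 42 × 3 / 0.5 = 10.08 | 2, 80 | 80.3% |
| 2a | 0.20 | 3 | 40 | 9.60 | 2, 76 | 78.2% |
| 2d | 0.17 | 2 | 70 | 0.0289 × 70 × 2 / 0.5 = 8.09 | 1, 68 | 80.1% |
| 2d | 0.17 | 2 | 68 | 7.86 | 1, 66 | 78.9% |

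Both stated figures come out exactly. A one-tailed .05, entered as an F test at .10, would give 34 and 56 instead, so the plan's numbers were evidently produced with the ordinary F test at .05.

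**Step 2: the same settings for 2e** (f = 0.50, m = 2).

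| N | λ = 0.25 × N × 2 / 0.5 | df | Power |
|---|---|---|---|
| 10 | 10 | 1, 8 | 79.1% |
| 11 | 11 | 1, 9 | 83.9% |
| 12 | 12 | 1, 10 | 87.6% |
| 16 | 16 | 1, 14 | 96.0% |

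The smallest total in equal groups is 12, against the stated 16. Power at 16 is 96.0%, against the stated 80%.

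**Step 3: what would give 16 at f = 0.50?**

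| Change of input | Result | Fit with the plan |
|---|---|---|
| ρ = 0.2 | 16 (83.6%; 14 gives 77.5%) | Not stated; would turn 42 and 70 into 66 and 112 |
| Four groups | 16 (82.2%) | The stated design is 2 × 2 |
| 95% power target | 16 (96.0%; 15 gives 94.7%) | The plan says 80% |
| F test at .01 | 16 (82.6%) | The plan says .05 |
| One-tailed .05 (F test at .10) | 8 (80.2%) | Moves further from 16 |

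**Step 4: outcomes against effects.**

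| 2e outcome | Planning effect in section 2.7 |
|---|---|
| Mean duration of continuous REM segments | f = 0.50, from prazosin on mean REM period duration; how period maps to segment is not stated |
| SWS minutes | None |

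**The case against.** **The correlation is unstated, so the settings are inferred.** This stands. Two exact matches make ρ = 0.5 a strong inference, but a different ρ could have been used for 2e alone. A reader might infer that the effect, the number or the power must be wrong. The documents do not go that far. What they show is that the three do not fit together under the settings behind 42 and 70, and that the inputs needed to settle the matter are missing.

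**The discrepancy is in the safe direction.** This also stands under the inferred settings: 16 exceeds 12, and the sentence claims only that 16 is sufficient. It would not be an argument for simply writing 12. At N = 12, power falls to 75% if ρ = 0.3 and to 60% if ρ = 0. There is also a possible error the other way. Suppose f = 0.50 was obtained as d/2 from a between-group d of 1.0 on change scores. This is an assumption, although the plan pairs d and f in that way for 2a. A t-test on change would then need 34 in total two-sided or 28 one-sided, and 16 would give 46% or 60% power.

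**The REM effect may well be the right measure.** A reader might infer from the two terms, REM period and REM segment, that the effect belongs to a different measure. The documents do not support that. They do not define REM period as the prazosin study used it, and section 2.2 uses REM sleep periods for the same consolidation of fragmented REM that 2e sets out to test. A mismatch is possible but not shown. The plan simply does not say how one maps to the other.

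**Little depends on it.** Hypothesis 2e is labelled exploratory, and nothing in the plan uses 16 as a threshold. This stands and fixes the weight of the point. It does not answer the absence of an SWS effect, which depends on no inferred setting.

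**Conclusion.** The point holds as a minor correction. Under an interaction F test at .05 with ρ = 0.5, inferred from the exact reproduction of 42 and 70, f = 0.50 needs 12 participants for 80% power, and 16 gives about 96%. The documents do not show which input produced the 16. Independently of that, the 80% has no basis for SWS, one of the two outcomes of 2e.

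This does not show that the trial is too small. The trial size rests on 2d: the 70 participants expected to be retained equal the 2d requirement.

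**What to change.** Rewrite the 2e power sentence in section 2.7 so that it states ρ, the number of groups, the tails and the power target, and so that N and power agree. For example: 16 participants give about 96% power at f = 0.50 with two groups, ρ = 0.5 and an F test at .05, and 12 would suffice for 80% under those same assumptions. The figure of 12 should not appear without its assumptions.

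Limit the statement to REM duration, add a line on how the prazosin REM period effect relates to this trial's REM segment measure, and make no power claim for SWS.

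Do not keep the 16 by pairing it with f = 0.40. It is the smallest even total at that effect (84.5%), but the only 0.40 among the plan's effect sizes is for prazosin on PTSD severity, so this would fit an effect to the number.

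The cost is a few sentences of text, with no change to the sample size or the analysis.
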